- Adverse Event or Device Deficiency eCRF, if applicable.

F.3.17 **Early Termination visit:**

Whenever possible, the study staff will perform an Early Termination visit when a subject decides to withdraw from the study early or if the subject is withdrawn early upon decision of investigator (during a normal study visit or an unscheduled visit).

Early Termination Procedures:

- Upload the MiniMed 640G into CareLink Clinical. Use correct Subject ID (311-XXX-XXX).
- Upload GST3C transmitters using GST3C Download utility, if applicable. Use correct Subject ID (Subject ID_XXXX_DATE).
- Collect blood sample for HbA1c at local lab, if applicable
- Ask subject to complete Clarke questionnaire, if applicable
- Ask subject to complete Gold questionnaire, if applicable. Ask Subject to complete HFS questionnaire, if applicable
- Ask subject to complete DTSQs and DTSQc questionnaires, if applicable
- Review adverse event or device deficiency, if any
- Retrieve all study related devices and material .

Early Termination Data collection:

- Unscheduled Visit eCRF, if withdrawal occurred in between scheduled study visits.
- Study Exit eCRF: with date and reason for withdrawal; last available HbA1c value, if applicable,
- Subjects Products Tracking log eCRF to record all returned devices and dates.
- Pump data upload in CareLink Clinical.
- Transmitter data upload using GST3C Download utility, if applicable
- Clarke eCRF, if available.
- Gold eCRF, if available
- HFS eCRF, if available.
- DTSQs eCRF, if available.
- DTSQc eCRF, if available.
- Adverse Event or Device Deficiency eCRF, if applicable.

F.4 Role of the sponsor's representatives

Sponsor's representatives may provide technical support following routine practice in the participating countries (i.e. pump or CGM training) and for study specific activities (i.e. data uploads, IT support). In the applicable participating sites where sponsor is involved in subject device trainings, the sponsor's representatives providing technical support will be listed on the sponsor technical support list.

F.5 Source documents

The patient's hospital/clinic file, CareLink data, HbA1c laboratory reports, data collected on the paper questionnaires are handled as source data.

The investigator will mark the clinical records to indicate that the subject is enrolled in this clinical study.

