- Review all reported SAE, SADE, UADE, Severe Hypoglycemia, Severe Hyperglycemia, DKA and deaths, and determines event classification (e.g. seriousness, severity, relatedness to device and procedure, unanticipated/anticipated) on a periodic basis.
- Upon request advise Sponsor about the potential clinical impact of an observed unintended device performance.
- Advise Sponsor in cases of SADEs.

A CEC charter will be established to indicate explicit rules outlining the minimum amount of data required and the algorithm followed in order to classify/adjudicate an event.

The CEC will assess these events to determine agreement or disagreement with the Investigator classification of the event. CEC decisions will be documented in meeting minutes. The Sponsor will notify the Investigator of any disagreement in assessment of an event by the CEC.

All other events will be reviewed and classified by the Sponsor's qualified internal safety individual(s) to ensure they should not be adjudicated by the CEC and that the events are appropriately classified by the investigator.

F.6.7 Data Safety Monitoring Board

The purpose of a data monitoring committee is to protect the safety of trial participants, the credibility of the study and the validity of study results. An independent Data Safety Monitoring Board (DSMB) will reassess the study sample size at the moment of the planned interim analysis.

The DSMB is established by the sponsor to oversee the following responsibilities:

- Review the interim analysis of effectiveness and safety measures after 60 subjects(30 treatment and 30 control group) have been randomized and followed up for 6 months.
- Following predefined rules in the DSMB chart, implement the assessment of modifications to the trial design.
The primary planned modification is a sample size re-estimation.
- Monitor baseline comparability.
- Monitoring adverse events: review aggregate subject data.
- Provide recommendations to continue or terminate the trial depending upon these analyses.

F.6.8 Emergency contact details in case of serious AEs

In case of an immediately reportable Adverse Event the investigators can contact the Medtronic study manager. Should the team members change during the course of the study, you may contact the current study manager.

F.7 Subject accountability

Subjects who are unwilling to participate in the follow up visits or complete study procedures should be withdrawn.

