If a subject is withdrawn from the clinical study, the reason for withdrawal shall be recorded in the eCRF and in the subject's hospital/clinic record. If discontinuation is because of safety, the subject shall be asked to be followed to collect safety data outside the clinical study.

In case follow-up visits are missed, a study deviation should be completed on the eCRF to document this.

If a subject does not return to the site for required follow-up visit(s) and cannot be reached, the investigation site personnel should make 3 attempts to contact the subject by phone to verify if the subject should be considered "lost-to follow up". In the event the subject is not able to perform follow-up visits at the investigation site, subject will be considered "lost to follow up" and this needs to be documented in the Study Exit eCRF.

F.8 Study deviations and CIP changes

A study deviation is an event where the investigator or investigation site personnel did not conduct the clinical study according to the Clinical Investigation Plan or Clinical Investigation Agreement. The investigator is not allowed to deviate from the above mentioned documents except with prior approval and under emergency circumstances. All deviations shall be documented and explained, regardless the reason for the deviation.

Medtronic will assess the significance of all deviations and evaluate the need to amend the Clinical Investigation Plan or to early terminate the investigation, in accordance with Medtronic SOPs.

F.8.1 Request for approval of study deviations

The investigator shall obtain documented approval from Medtronic, before implementation, for any change in- or deviation from the Clinical Investigation Plan. In case of study deviations that can affect the subject's rights, safety and well-being or the scientific integrity of the clinical study, approval from the EC/IRB and regulatory authority must also be obtained before implementation. The investigator shall timely contact the Clinical Study Manager for review of the proposed change/deviation.

Prior approval is not always realistic in situations where unforeseen circumstances are beyond the investigator's control. However, also in these cases, the event is considered a deviation, and shall be reported.

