- Detailed description of the Intention To Treat (ITT) analysis: Analysis will be performed on the Intent to Treat (ITT) basis. The ITT set will be composed of randomized subjects who underwent at least two week of CGM (blinded CGM in the Control arm and unblinded CGM in the Treatment arm). These subjects will be followed up, assessed and analyzed as members of the intended randomized arm, irrespective of their compliance to the planned course of treatment or deviations from protocol. Imputation of missing data in the ITT analysis will be performed using multiple imputation.
- Additional ad-hoc analysis may be performed and will be described as such in the report of study results.

H.2 Publication Policy

Publications and presentations referring to this clinical study will be coordinated by Medtronic with the Study Steering Committee to allow the use of all available data. The following publication policy will have to be adhered to by all participating investigation sites.

Medtronic intends to publish the results of the clinical study in a scientific journal.

A separate Publication Plan will describe the publication strategy and processes for publications of the SMILE study.

Authorship on any publication(s) resulting from this clinical study will be assigned according to substantial contributions to conception and design, acquisition of data, or analysis and interpretation of data, drafting the article or revising it critically for important intellectual content, final approval of the version to be published and agreement to be accountable for all aspects of the work in ensuring that questions related to the accuracy or integrity of any part of the work are appropriately investigated and resolved. This is in accordance with the International Committee of Medical Journal Editors (ICMJE) published guidelines (JAMA 2013), as agreed upon by the editors of all major medical journals.

The number of authors will be dependent on the regulations of the concerning journal with a maximum of 10 authors. Names of all participating investigators will appear in the Acknowledgment of the paper.

Based on the principle that Medtronic owns the data of this clinical study, a single investigation site may access and use the data provided by itself for scientific publications following prior approval by the Steering Committee.

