7.1.3. Analysis Sets

7.1.3.1. Efficacy analysis set

For the primary endpoint, efficacy analyses will be performed in the Intent to Treat (ITT) basis. The ITT set will be composed of all randomized subjects. These subjects will be assessed and analyzed as members of the intended randomized arm, irrespective of their compliance to the planned course of treatment or deviations from protocol.

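### Protocol F.7 withdraws subjects who refuse a study procedure, which conflicts with the follow-up promised in Protocol H.1 and loses outcomes that could still be collected

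*Protocol*

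**What the plan says.** Protocol F.7 (Subject accountability) gives sites this rule: "Subjects who are unwilling to participate in the follow up visits or complete study procedures should be withdrawn".

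Protocol H.1 (Analysis of clinical data) says that subjects in the intention-to-treat (ITT) set will be "followed up, assessed and analyzed as members of the intended randomized arm, irrespective of their compliance to the planned course of treatment". H.1 limits that set: "The ITT set will be composed of randomized subjects who underwent at least two week of CGM".

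SAP 7.1.3.1 widens the set: "The ITT set will be composed of all randomized subjects". It has them assessed and analysed in their randomised arm "irrespective of their compliance to the planned course of treatment or deviations from protocol", but it does not say that they will be followed up.

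Two places describe what happens after withdrawal. Protocol F.3.17 provides an early termination visit, where possible, with data uploads, adverse event review and, where applicable, HbA1c and questionnaires. Staff are then to "Retrieve all study related devices and material". For later contact, F.7 says only: "If discontinuation is because of safety, the subject shall be asked to be followed to collect safety data outside the clinical study".

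SAP 7.4 analyses the primary endpoint with a mixed model on available data, on the footing that missing data may be missing at random. SAP 7.12 records that this replaces the multiple imputation named in the protocol.

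**The concern.** F.7 treats refusal of a procedure as a reason to leave the study. H.1 treats non-compliance as something that follow-up should survive. Sensor wear is a study procedure, and in the treatment arm it is also the therapy. A treatment-arm subject who no longer wants continuous sensing, but would accept HbA1c tests, questionnaires or a short blinded recording, falls under F.7 and leaves.

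Withdrawal for this reason may be related to how the subject would have done. If it is, the later periods are not missing at random given the data in hand, and the mixed model does not correct for that. The estimate then describes something other than the effect in all randomised subjects. HbA1c, questionnaire and adverse event data due after withdrawal are lost as well.

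**Working it through.** **1. Do F.7 and H.1 conflict?** Yes, for a subject with at least two weeks of CGM who refuses a procedure: F.7 withdraws the person, H.1 follows the person up. A subject who refuses before two weeks of CGM is outside H.1's promise but inside the SAP's ITT set. SAP 7.1.3.1 is not contradicted. It keeps withdrawn subjects in their arm and makes no promise of follow-up.

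**2. Who is affected?** Three provisions keep ordinary non-adherence inside the study:
- Protocol F.2.1 makes low sensor use a reported deviation, and the visit procedures (for example F.3.9) provide retraining.
- Protocol F.7 itself makes a missed visit a deviation.
- SAP 7.1.2 removes low users from the per-protocol set only, and lists dropping out as a separate criterion.

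A subject who refuses all sensor wear gives no primary outcome, withdrawn or not. What remains are subjects who refuse the therapy or one procedure but would still provide other outcomes. The documents give no rate for them.

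**3. What is lost?** Primary data come from three 2-week periods starting at weeks 10, 16 and 22 (SAP 7.7.2). A subject withdrawn before week 10 has no post-baseline primary outcome. A later withdrawal loses the remaining periods. The primary-endpoint sensitivity analyses in the SAP are the per-protocol set, which also excludes dropouts, and an optional square-root transformation (SAP 7.9.1). Neither examines informative withdrawal.

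**4. The plan's own figures.** Inputs from SAP 6.2: control mean 2, SD 1.65, 40% reduction, two-sided alpha 0.05, power 80%, dropout 15%.
- Difference: 0.40 × 2 = 0.80 events per week.
- The t-test calculation gives 67.75, so 68 per arm and 136 completers, as stated.
- 136 / 0.85 = 160 randomised, as stated.
- Allowance for loss: 0.15 × 160 = 24 subjects over both arms and all causes, or 12 per arm if split evenly.

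**5. Illustration.** These assumptions are not in the documents. A fraction f of the treatment arm is lost through refusal, has no usable data in any period, and would have had the control rate. Those retained show the full 0.80, and nothing offsets this in the control arm. The all-randomised difference is 0.80 × (1 − f).

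| f | All-randomised difference | Retained minus all-randomised | Ratio |
|---|---|---|---|
| 0% | 0.80 | 0 | 1.00 |
| 5% | 0.76 | 0.04 | 1.05 |
| 10% | 0.72 | 0.08 | 1.11 |
| 15% | 0.68 | 0.12 | 1.18 |

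If half the effect persisted in those lost, the difference at f = 15% would be 0.85 × 0.80 + 0.15 × 0.40 = 0.74. The 15% row assigns every planned treatment-arm loss to this one cause.

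**The case against.** The strongest reply is that the protocol already keeps non-adherent subjects. F.7 speaks of unwilling subjects, low sensor use and missed visits are deviations, and the SAP retains everyone randomised in the ITT set. Run-in also screens out people who do not tolerate the sensor before randomisation (Protocol D.3, J.3). The early termination visit collects a last set of outcomes, safety discontinuations are asked for further safety data, and the model uses every earlier period. All of this stands and narrows the point. It does not provide efficacy follow-up after withdrawal, and the documents do not tell unblinded site staff where a deviation ends and unwillingness begins.

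A reader might infer that F.7 turns non-adherence in general into missing outcomes, or that it contradicts SAP 7.1.3.1. Steps 1 and 2 of the working show that the documents support neither reading.

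A reader might also infer that the treatment effect must be overstated, because continuous sensor wear is a heavier burden than the controls' six weeks of blinded recording. That direction is not established. The trial is open-label. Protocol J.1 says controls may get no benefit, while treatment subjects gain access to CGM that may not be reimbursed, and controls wear sensors whose readings they cannot see. Differential loss could run either way.

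**Conclusion.** The concern holds in a limited form. F.7 and H.1 need to be reconciled, because F.7 as written loses outcomes that some subjects would still give, and the primary analysis has no protection if that loss is informative.

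The size is unknown. Under the stated assumptions the gap between the difference in retained subjects and the all-randomised difference runs from 0 to 0.12 events per week. The upper end (a ratio of 1.18) is an extreme case, not an expected bias: it needs all treatment-arm loss to be refusal of this kind, full reversion to the control rate, no usable data in any period and no offsetting loss among controls. The sample size is not at issue here; 136 and 160 follow from the SAP's inputs.

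**What to change.** Amend F.7 so that stopping a device or procedure is distinct from leaving the study. A subject who stops a procedure stays in whatever scheduled outcome collection he or she is willing to give: HbA1c, questionnaires, adverse events and, if willing, the three 2-week blinded recordings. Follow-up ends only on withdrawal of consent or loss to follow-up. Align F.3.17 with this, so that retrieving devices does not rule out later recordings, and state in H.1 and SAP 7.1.3.1 that follow-up continues on this basis.

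The cost is an amendment plus some recorder dispensing, refresher training and transmitter uploads for a few treatment-arm subjects; in the treatment phase these steps are now specified for controls only. The visits are already scheduled, and every subject has used the blinded recorder in run-in. The change concerns data collection only. It sets no rule on when therapy stops and leaves the right to withdraw consent untouched. It will not recover primary outcomes from subjects who refuse all sensor wear.

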The names and addresses of sponsor team, monitors, investigators and participating investigational centers will be kept under separate cover. These lists will be provided to the participating investigators and sponsor shall inform the investigators in case changes occur in the list of participating sites. The most current lists of the contact persons (Sponsor List ; Monitors List ; Investigators List) are available upon request.

L.2 Case Report Forms

The Case Report Form is provided under a separate cover upon request to the Sponsor.

L.3 Sample Investigator Agreement

Sample Investigator Agreement will be provided under a separate cover upon request to the Sponsor.

L.4 List of consumables

INFUSION SETS EUROPE

MMT-399	MiniMed™ Quick-set™ 60cm tubing with 6 mm cannula (box of 10)
MMT-387	MiniMed™ Quick-set™ 80cm tubing with 6 mm cannula (box of 10)
MMT-398	MiniMed™ Quick-set™ 110cm tubing with 6 mm cannula (box of 10)
MMT-397	MiniMed™ Quick-set™ 60cm tubing with 9 mm cannula (box of 10)
MMT-386	MiniMed™ Quick-set™ 80cm tubing with 9 mm cannula (box of 10)
MMT-396	MiniMed™ Quick-set™ 110cm tubing with 9 mm cannula (box of 10)
MMT-921/941	MiniMed™ Mio™ 45cm tubing with 6mm cannula (Pink/Blue) (box of 10)
MMT-923/943	MiniMed™ Mio™ 60cm tubing with 6mm cannula (Pink/Blue) (box of 10)
MMT-965	MiniMed™ Mio™ 80cm tubing with 6mm cannula (box of 10)
MMT-975	MiniMed™ Mio™ 80cm tubing with 9mm cannula (box of 10)
MMT-368	MiniMed™ Silhouette™ 45cm tubing with 13mm cannula (box of 10)
MMT-381	MiniMed™ Silhouette™ 60cm tubing with 13mm cannula (box of 10)
MMT-383	MiniMed™ Silhouette™ 80cm tubing with 13mm cannula (box of 10)
MMT-382	MiniMed™ Silhouette™ 110cm tubing with 13mm cannula (box of 10)
MMT-378	MiniMed™ Silhouette™ 60cm tubing with 17mm cannula (box of 10)
MMT-384	MiniMed™ Silhouette™ 80cm tubing with 17mm cannula (box of 10)
MMT-377	MiniMed™ Silhouette™ 110cm tubing with 17mm cannula (box of 10)
MMT-864	MiniMed™ Sure-T™ 60cm tubing with 6mm cannula (box of 10)
MMT-866	MiniMed™ Sure-T™ 80cm tubing with 6mm cannula (box of 10)
MMT-874	MiniMed™ Sure-T™ 60cm tubing with 8mm cannula (box of 10)
MMT-876	MiniMed™ Sure-T™ 80cm tubing with 8mm cannula (box of 10)
MMT-884	MiniMed™ Sure-T™ 60cm tubing with 10mm cannula (box of 10)
MMT-886	MiniMed™ Sure-T™ 80cm tubing with 10mm cannula (box of 10)
MMT-905	MiniMed™ Mio™ 30 60cm tubing with 13mm cannula (box of 10)
MMT-906	MiniMed™ Mio™ 30 100cm tubing with 13mm cannula (box of 10)

INFUSION SETS CANADA

MMT-921600	MiniMed™ Mio Pink 18" tubing with 6mm cannula (box of 10)
MMT-941600	MiniMed™ Mio Blue 18" tubing with 6mm cannula (box of 10)
MMT-923600	MiniMed™ Mio Pink 23" tubing with 6mm cannula (box of 10)
MMT-943600	MiniMed™ Mio Blue 23" tubing with 6mm cannula (box of 10)
MMT-965600	MiniMed™ Mio Clear 32" tubing with 6mm cannula (box of 10)
MMT-975600	MiniMed™ Mio Clear 32" tubing with 9mm cannula (box of 10)
MMT-905600	MiniMed™ Mio30 23" tubing with 13mm cannula (box of 10)
MMT-900660	MiniMed™ Mio30 43" tubing with 13mm cannula (box of 10)
MMT-394600	MiniMed™ Quick Set 18" tubing with 6 mm cannula (box of 10)
MMT-399600	MiniMed™ Quick Set 23" tubing with 6 mm cannula (box of 10)
MMT-387600	MiniMed™ Quick Set 32" tubing with 6 mm cannula (box of 10)
MMT-398600	MiniMed™ Quick Set 43" tubing with 6 mm cannula (box of 10)
MMT-397600	MiniMed™ Quick Set 23" tubing with 9 mm cannula (box of 10)
MMT-386600	MiniMed™ Quick Set 32" tubing with 9 mm cannula (box of 10)
MMT-396600	MiniMed™ Quick Set 43" tubing with 9 mm cannula (box of 10)
MMT-368600	MiniMed™ Silhouette 18" tubing with 13mm cannula (box of 10)
MMT-381600	MiniMed™ Silhouette 23" tubing with 13mm cannula (box of 10)
MMT-383600	MiniMed™ Silhouette 32" tubing with 13mm cannula (box of 10)
MMT-382600	MiniMed™ Silhouette 43" tubing with 13mm cannula (box of 10)
MMT-378600	MiniMed™ Silhouette 23" tubing with 17mm cannula (box of 10)
MMT-384600	MiniMed™ Silhouette 32" tubing with 17mm cannula (box of 10)
MMT-377600	MiniMed™ Silhouette 43" tubing with 17mm cannula (box of 10)
MMT-862	MiniMed™ Sure-T 18" tubing with 6mm cannula (box of 10)
MMT-864	MiniMed™ Sure-T 23" tubing with 6mm cannula (box of 10)
MMT-874	MiniMed™ Sure-T 23" tubing with 8mm cannula (box of 10)

INFUSION SET INSERTION DEVICES

MMT-395	MiniMed™ Quick-serter™ (for use with Quick Set Infusion Sets)
MMT-385	MiniMed™ Sil-serter™ (for use with Silhouette Infusion Sets)

RESERVOIRS

MMT-326A	1.8 mL reservoirs (box of 10)
MMT-332A	3.0 mL reservoirs (box of 10)

OTHERS

ACC-LR6	AA Battery (Alkaline)
MMT-174	Tape HMS-174 ADH IV3000 1-hand 13L
7005739-006	Standard tape
HMS-180	Skin Tac Adhesive Wipe (box of 50)
MMT-173	Skin preparation wipes

L.5 Sample Questionnaires

The Clarke, Gold, HFS and DTSQ questionnaires are available in local language and will be provided under a separate cover upon request to the Sponsor.

L.6 Abbreviations

ADE	Adverse Device Effect
AE	Adverse event
CEC	Clinical Events Committee
AUC	Area Under the Curve
BG	Blood Glucose
BP	Blood pressure
CIP	Clinical Investigation Plan
C	Control Arm
CGM	Continuous Glucose Monitoring
CRF	Case Report Form
CSII	Continuous Subcutaneous Insulin Infusion
d	day
DD	Device Deficiency
DM	Diabetes Mellitus
DMC	Data Monitoring Committee
EC	Ethical Committee
eCRF	Electronic Case Report Form
EDC	Electronic Data Capture (Oracle Clinical)
FDA	Food and Drug Administration
FU	Follow up
HFS	Hypoglycemia Fear Survey
IFU	Instruction For Use
ICH-GCP	International Conference on Harmonization – Good Clinical Practice
IRB	Institutional Review Board
ISF	Investigator Site File
m	months
MAGE	Mean Amplitude Glucose Excursion
MDD	Medical Device Directive
MDI	Multiple Daily Injection
PIC	Patient Informed Consent
PRO	Patient Reported Outcome
RA	Regulatory Affairs
RAE	Regulatory Affairs Europe
SADE	Serious Adverse Device Effect
SAE	Serious Adverse Event
SAP	Sensor Augmented Pump
SMBG	Self-Monitoring Blood Glucose
SOP	Standard operating procedure
T	Treatment arm
T1DM	Type 1 Diabetes Mellitus
USADE	Unanticipated Serious Adverse Device Effect
w	week
WECAN	West Europe and Canada
yrs	Years
